ARISE: Evaluation of the GORE® Ascending Stent Graft in the Treatment of DeBakey Type I/II Aortic Dissection (TBE 14-02)

NCT02380716

Protocol V7 Approval Date: 15 Sept 2020

Statistical Analysis Plan Date: 09 Jun 2021

Nothing herein is to be disclosed in any way without the prior express written permission of W. L. Gore & Associates, Inc.

ARISE: Evaluation of the GORE® Ascending Stent Graft in the Treatment of DeBakey Type I/II Aortic Dissection

Protocol Number: TBE 14-02

Amendment 7

15 Sept 2020

W. L. Gore & Associates, Inc. Medical Products Division

PROTOCOL SUMMARY

O. 1 700				
Study Title	ARISE: Evaluation of the GORE® Ascending Stent Graft in the Treatment of DeBakey Type I/II Aortic Dissection			
Protocol Number	TBE 14-02			
IDE or PMA Number	G140230			
Sponsor	W. L. Gore & Associates, Inc. Medical Products Division [contact]			
Study Design	Prospective, multicenter, non-randomized, single arm study			
Study Objective	Assess the feasibility of the treatment of DeBakey Type I/II aortic dissections with the GORE® Ascending Stent Graft			
Study Endpoints	Primary Endpoint: • All-cause mortality at 30 days post-procedure			
	 Secondary Endpoints: Successful dissection treatment (technical success), to include: Successful access to the aorta (transfemoral or retroperitoneal) Successful delivery of all required device components to the aorta and/or branch vessel Successful deployment of all required device components in their intended location Successful retrieval of device delivery system Exclusion of the primary entry tear of the aortic dissection based on completion angiography Patent Side Branch Component (if used as part of primary procedure) based on completion angiography Major Adverse Cardiovascular and Cerebrovascular Event (MACCE) assessed through 30 days, 6 months, and 12 months Individual MACCE components through 30 days, 6 months, and 12 months Aorta related mortality Device migration assessed through 1 month, 6 months, and 12 months Endoleak assessed through 1 month, 6 months, and 12 months 			
Subject Population	Subjects with DeBakey Type I/II aortic dissection allowing for treatment with the GORE® Ascending Stent Graft, including: • Primary entry tear must be in the ascending aorta and ≥2cm distal to the most distal coronary artery			
	ostia			

	 Ascending aorta compatible with the GORE® Ascending Stent Graft including landing zone true lumen diameter between 27mm – 42mm and total aortic landing zone diameter ≤ 45 mm 			
Number of Subjects	Up to 30 subjects			
Number of Sites	Up to 9 sites in the U.S.			
Significant Inclusion Criteria	DeBakey Type I/II aortic dissection compatible with the treatment requirements of the GORE® Ascending Stent Graft, including:			
	 ○ Primary entry tear must be in the ascending aorta and ≥2cm distal to the most distal coronary artery ostia 			
	 Ascending aorta compatible with the GORE® Ascending Stent Graft including landing zone true lumen diameter between 27mm – 42mm and total aortic landing zone diameter ≤ 45 mm 			
	Able to undergo CT scan per protocol requirements to perform required case planning prior to endovascular procedure			
	High surgical risk, as determined by the implanting physician			
	An Informed Consent Form signed by subject or legally authorized representative			
Significant Exclusion Criteria	Planned aortic valve repair or replacement or coronary artery intervention within 30 days			
	Presence of mechanical heart valve in the aortic position			
	Primary entry tear location in the aortic arch or descending thoracic aorta with retrograde flow into the ascending aorta			
	Aortic insufficiency grade 3+ or 4+			
	Life expectancy <12 months due to associated non- cardiac co-morbid conditions			
Expected Time to Complete Enrollment	 Subject accrual: 2 years Follow-up: 5 years from last subject enrollment Total study duration: 7 years 			
Schedule of Events	Screening: Surgical Risk Assessment, Spiral CTA of chest, abdomen and pelvis (Retrospective cardiac-gated CTA Scan optional), Physical Exam, Serum Creatinine, SF-36® Questionnaire, Transthoracic Echocardiogram and Modified Rankin Scale			
	 Procedure: Endovascular procedure with post-treatment Angiogram and Transesophageal Echocardiogram Post-procedure: Transthoracic or Transesophageal Echocardiogram ≤ 2 hours after procedure end time 			

- Discharge: Physical Exam, Transthoracic Echocardiogram and Modified Rankin Scale
- 1 month and 6 months post-treatment: Retrospective cardiac-gated CTA Scan with ≥10 cardiac phases of chest, Physical Exam, SF-36[®] Questionnaire, Transthoracic Echocardiogram and Modified Rankin Scale
- Modified Rankin Scale also completed at 90 days for subjects suspected of experiencing a stroke event through 30 days
- 12 month post-treatment: Retrospective cardiac gated CTA Scan of chest, SF-36[®] Questionnaire, Transthoracic Echocardiogram and Physical Exam

1.0 Introduction

This Statistical Analysis Plan (SAP) describes the statistical analyses planned to address the objectives of the evaluation of the GORE® Ascending Stent Graft in the treatment of DeBakey Type I/II aortic dissections (TBE 14-02).

2.0 Study Design Overview

2.1 **Objectives**

2.1.1 Primary Objective(s)

- To assess the feasibility of treating DeBakey Type I/II aortic dissections with the GORE® **Ascending Stent Graft**
- 2. Refine patient selection for future clinical investigations
- 3. To estimate boundary conditions in DeBakey Type I/II aortic dissection patients which can be used for subsequent device development efforts including:
 - Aortic compliance
 - Cardiac and respiratory motion

2.2 **Design Summary**

This study is a prospective, multicenter, non-randomized single-arm study to assess the feasibility of the treatment of DeBakey Type I/II aortic dissections with the GORE® Ascending Stent Graft Device.

A maximum of 9 Clinical Investigative Sites (referred to as "Sites" in the remainder of this document) in the United States will participate in this study. A total of 30 patients will be enrolled in this study.

Patients may be enrolled into the study provided all inclusion and no exclusion criteria are met as specified in Section 4 of the study Protocol.

2.3 **Study Endpoints**

2.3.1 **Primary Endpoint**

The primary endpoint is all cause mortality through 30 days post-procedure.

2.3.2 **Secondary Endpoints**

Secondary endpoints include the following:

- Successful dissection treatment (technical success), to include:
 - Successful access to the aorta (transfemoral or retroperitoneal)
 - Successful delivery of all required device components to the aorta and/or branch vessel
 - Successful deployment of all required device components in their intended location

CONFIDENTIAL INFORMATION

MD133254 Statistical Analysis Plan Template

- o Successful retrieval of device delivery system
- Exclusion of the primary entry tear of the aortic dissection based on completion angiography
- Patent Side Branch Component (if used as part of primary procedure) based on completion angiography
- Major Adverse Cardiovascular and Cerebrovascular Event (MACCE) assessed through 30 days, 6 months, and 12 months.
- Individual MACCE components through 30 days, 6 months, and 12 months.
- Aorta-related mortality
- Device migration assessed at 1 month, 6 months, and 12 months
- Endoleak assessed at 1 month, 6 months, and 12 months

2.3.3 Endpoint Definitions

MD133254 Statistical Analysis Plan Template

2.4 Statistical Hypotheses

No formal statistical tests will be performed. Data will be presented descriptively with confidence intervals.

2.5 Sample Size Assumptions

2.6 Sample Size Calculations

3.0 **Study Treatment Arms**

3.1 **Test Arm**

The test arm are those Subjects enrolled in this study for the treatment of DeBakey Type I/II aortic dissections (see Section 4 of the study Protocol).

3.2 **Control Arm**

There is no control arm in this study.

4.0 **Study Data Collection**

4.1 **Data Collected**

Data will be collected in Case Report Forms (CRFs) and include the following:

- Demographics
- · Eligibility (Inclusion/Exclusion) Criteria
- Medical History
- Risk Assessment
- · Subject Physical Evaluations and Vitals
- · Modified Rankin Scale Assessments
- SF-36® Questionnaire
- · Pre-Imaging Assessment
- Treatment Assessment
- Interval (Post) Imaging Assessments
- Device Accountability (Treatment and Post-Treatment)
- Planned Interventions
- · Study Completion/Discontinuation/Compliance
- Adverse Events (AEs) and Treatments (including Reinterventions)
- · Clinical Events Committee (CEC) Evaluations

[figure not shown]

CONFIDENTIAL INFORMATION

MD133254 Statistical Analysis Plan Template

Revision#: 1 Doc Type: GC Page 6 of 17

4.2 Follow-up windows

[figure not shown]

4.3 Schedule of Events

CONFIDENTIAL INFORMATION

MD133254 Statistical Analysis Plan Template Revision#: 1

Doc Type: GC

MD133254 Statistical Analysis Plan Template

4.4 Data Safety Monitoring Board

See Section 9.3 of the study Protocol.

4.5 Clinical Events Committee

See Section 9.4 of the study Protocol.

4.6 Imaging

5.0 Statistical Analyses

5.1 Analysis Populations

All enrolled Subjects with an attempted initial procedure (have non-missing initial procedure date) will be included in analysis as follows:

- Primary Endpoint: all Subjects will be included; Subjects without known mortality status through 30-days will be considered failures for this (i.e. assumed dead for the primary endpoint analysis).
- Secondary Endpoint of technical success: all Subjects will be included; any Subject missing evaluation on this will be counted as a failure for this endpoint.
- Secondary Endpoint (MACCE, MACCE components, and aorta-related mortality): all Subjects will be included.
- Secondary Endpoints (device migration, endoleak): Subjects with known status (have had imaging done or endpoint event reported) at each follow-up window will be included; an endpoint event (endpoint failure) will be reported from a Site-reported adverse event. Subjects without imaging reported in a window but with an adverse event meeting the endpoint definition in a window will count as having an endpoint event for that window. Subjects without imaging reported in a window and with no endpoint event reported in window will not count towards the denominator for that window.

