5.3 Analyses Supporting Primary Objective(s)

Primary and secondary endpoint analyses will be summarized for main reporting efforts in order to support the study objective. Analysis populations will be as described in Section 5.1.

5.3.1 **Primary Endpoint**

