5.3.3 Secondary Endpoint - MACCE

Kaplan Meier methodology will be used to estimate the overall MACCE event rate through the following specified time intervals: 30 days, 180 days (6 months), and 365 days (12 months). A Subject experiencing a MACCE event will have their time be equal to their earliest MACCE event onset; a Subject not experiencing a MACCE event will be censored at their last reported date of contact. This analysis will be performed for each MACCE component (see Endpoint Definitions Section 2.3.3) as well. Endpoint MACCE events will be death or CEC-adjudicated adverse events meeting the endpoint definitions (assessed on the CEC CRF). All possible adverse events that could meet the endpoint definition will be sent to the CEC for adjudication.

In addition to Kaplan Meier methodology, tables will be prepared with time intervals and the incident MACCE event rate will be reported in each time interval window. Denominators for the time windows will be the number of Subjects remaining in follow-up as of the beginning of the time interval window. Time intervals for these tables will be as follows: 0 days, 1-30 days, 31-180 days, 181-365 days, 366-731, 732-1096, 1097-1461, 1462-1826.

MD133254 Statistical Analysis Plan Template

5.3.4 **Secondary Endpoint – Aorta-Related Mortality**

The aorta-related mortality endpoint (see Endpoint Definitions Section 2.3.3) will be determined by CEC adjudication using a specific question asked on the CEC CRF.

For analysis of the aorta-related mortality endpoint, Kaplan Meier methodology will be used to estimate the aorta-related mortality rate through the following specified time intervals: 30 days, 180 days (6 months), and 365 days (12 months) and annually thereafter. Subjects without an aorta-related death reported before the end of the time period of interest will be censored at the Subject's last reported contact date or the end of the time period of interest, whichever date is earlier.

5.3.5 **Secondary Endpoints – Device Migration and Endoleak**

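### Does counting unknown 30-day status as death in the primary endpoint, but censoring it in MACCE, make the 30-day results unsound?

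*Combined protocol and SAP*

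**What the plan says.** SAP 5.1 sets the missing-data rule for the primary endpoint, all-cause mortality through 30 days: "Subjects without known mortality status through 30-days will be considered failures for this (i.e. assumed dead for the primary endpoint analysis". For the cardiovascular and cerebrovascular composite it says only "Secondary Endpoint (MACCE, MACCE components, and aorta-related mortality): all Subjects will be included", with no rule that treats missing status as failure.

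SAP 5.3.3 then gives two MACCE analyses.

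- **Kaplan-Meier** at 30, 180 and 365 days, in which "a Subject not experiencing a MACCE event will be censored at their last reported date of contact". It adds that "This analysis will be performed for each MACCE component" and that "Endpoint MACCE events will be death or CEC-adjudicated adverse events meeting the endpoint definitions".
- **A table by time window**, for which "Denominators for the time windows will be the number of Subjects remaining in follow-up as of the beginning of the time interval window". Its rows begin "Time intervals for these tables will be as follows: 0 days, 1-30 days, 31-180 days", so day 0 has a row of its own.

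SAP 5.3 brings the results together: "Primary and secondary endpoint analyses will be summarized for main reporting efforts in order to support the study objective". SAP 2.4 plans no formal tests, only descriptive results with confidence intervals.

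**The concern.** Take a subject last seen alive and event-free on day 10 whose status at day 30 is never learned. The primary analysis counts a death. Kaplan-Meier MACCE and its components censor the subject on day 10. The row for days 1 to 30 keeps the subject in the denominator and adds no event.

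Death is part of MACCE, so under one common rule 30-day MACCE cannot be lower than 30-day mortality. Under the stated rules it can be. A reader who sees both figures in one report might suspect an error, or might take the lower MACCE figure as the truer picture of risk. At 30 subjects, each unknown status adds 1/30 = 3.3 points to the primary rate, so one or two such subjects would show.

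**Working it through.** **Inputs.** N = 30 (SAP 2.2; the protocol summary says up to 30). The documents give no loss rate or expected event rate, so the remaining counts are assumptions:

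- d: known deaths by day 30
- u: unknown 30-day status, no recorded MACCE
- m: known survivors with a non-fatal MACCE
- v: unknown 30-day status after a recorded non-fatal MACCE

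The visible text has no planned figure to reproduce.

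**Formulas.**

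- Primary rate = (d + u + v)/N.
- Kaplan-Meier MACCE lies between (d + m + v)/N, when all u are censored after the last event, and (d + m + v)/(N − u), when all are censored before the first.
- Kaplan-Meier death with v = 0 lies between d/N and d/(N − u).
- Worst-case MACCE, with every unknown status an event = (d + m + u + v)/N. This exceeds the primary rate by m/N and so is never below it.

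**Results with d = 3, v = 0** (exact 95% intervals; the interval method is an assumption):

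| u | m | Primary | Kaplan-Meier MACCE | Kaplan-Meier death | Worst-case MACCE |
|---|---|---|---|---|---|
| 0 | 1 | 3/30 = 10.0% (2.1–26.5) | 4/30 = 13.3% | 10.0% | 13.3% |
| 1 | 0 | 4/30 = 13.3% (3.8–30.7) | 3/30 to 3/29 = 10.0–10.3% | 10.0–10.3% | 13.3% |
| 2 | 1 | 5/30 = 16.7% (5.6–34.7) | 4/30 to 4/28 = 13.3–14.3% | 10.0–10.7% | 6/30 = 20.0% |
| 2 | 2 | 5/30 = 16.7% (5.6–34.7) | 5/30 to 5/28 = 16.7–17.9% | 10.0–10.7% | 7/30 = 23.3% |

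**When the order reverses.** Kaplan-Meier MACCE is never below (d + m + v)/N, so mortality above MACCE requires u > m. With v = 0, a reversal whatever the censoring day also requires m < u(N − d − u)/N. For u = 2 and d = 3 the bound is 2 × 25/30 = 1.67, so m = 1 reverses and m = 2 does not.

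**Subjects lost after a MACCE.** They are events in both analyses and do not drive the reversal. With d = 3, u = 1, m = 0, v = 1, the primary rate is 5/30 = 16.7%, Kaplan-Meier MACCE is 4/30 to 4/29 = 13.3–13.8%, and worst-case MACCE is 5/30 = 16.7%.

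**The window row is not evidence.** The row for days 1 to 30 leaves out day 0, so it is not a rate through 30 days. With nothing missing, no non-fatal MACCE and three deaths, one of them on day 0, the primary rate is 3/30 = 10.0% and the row shows 2/29 = 6.9%. That difference comes from how the table is built and has nothing to do with unknown status.

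**Kaplan-Meier on both sides does not guarantee the order either.** Let one subject of 30 have a non-fatal MACCE on day 3 and die on day 20, and another be censored on day 10. Kaplan-Meier MACCE is 1/30 = 3.33% and Kaplan-Meier mortality is 1/29 = 3.45%. A small inversion can thus arise from ordinary censoring under a single rule.

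**The case for a change.** The strongest case for a change uses the death component. If death is analysed as a component, the report carries two values for 30-day death from any cause: 16.7% and 10.0–10.7% with d = 3 and u = 2. They differ whenever a subject without a recorded MACCE has unknown status and at least one subject is known alive at day 30; no condition on m is needed. The sponsor wrote a rule for unknown status and so foresaw it. In a purely descriptive study the reported rates are the main product, and a count of imputed deaths costs one line.

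The facts in this stand: if any status is unknown, the primary rate is a worst-case figure and should not be read as directly comparable with Kaplan-Meier MACCE or its death component. The step to a needed change does not. The two values answer different questions, one a bound under the worst assumption and the other an estimate under censoring, and SAP 5.1 says openly that the assumption is confined to the primary endpoint. Anyone holding the output can subtract reported deaths from the primary numerator to find how many were imputed: 5 − 3 = 2 in this example. The bodies of SAP 2.3.3, 5.3.1, 5.5.1 and 8.1 are not visible, and 5.5.1 is headed as a sensitivity analysis of endpoint results, so it cannot be said that a reconciling line is missing.

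**Conclusion.** The concern describes the rules correctly but does not call for a change. Using two methods is a fair trade-off. For a 30-day mortality proportion in 30 subjects, counting an unknown as dead is simple and cannot flatter the device. For a composite followed to 365 days, the same rule would turn every later loss into an event, so censoring is the usual choice.

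The effect is conditional. It is nil if every 30-day status is known. Otherwise each unknown adds 3.3 points to the primary rate, and mortality exceeds Kaplan-Meier MACCE only if event-free losses outnumber survivors with a non-fatal MACCE. In the d = 3, u = 2, m = 1 example the gap is 2.4 to 3.3 points (16.7% less 14.3% or 13.3%), well inside the primary rate's own interval of 5.6% to 34.7%. No test is planned, and no visible decision rule uses the order of the two rates.

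This rests on assumed values of d, u, m and v and on the visible text alone. Naming the number of imputed deaths beside the primary rate, or showing a worst-case MACCE line of (d + m + u + v)/N, would be an optional clarification in the report. Neither corrects an error in the plan.

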5.2 Timing of Analyses

Analysis of the study results will be ongoing throughout enrollment. Regular case review by the Data and Safety Monitoring Board (DSMB) and Sponsor will occur throughout enrollment.

DSMB data review will be instituted as follows:

- For the first four (4) Subjects, procedural reports will be provided to FDA and the DSMB Chairman within 5 working days of endovascular treatment and will include available procedural narratives, reports and any preliminary Adverse Events (AEs.
- Reporting Subject and device performance data to the DSMB following the endovascular treatment of every two (2) Subjects through patient 20 and every five (5) patients for patient 20-30, including the available 1 month follow-up visit data for preceding cohorts.

- Reports will include information on Subject baseline characteristics, deaths, and a summary of all serious adverse events such as paraplegia, paraparesis, stroke, and aortic rupture.
- Reports will also include observed device and/or procedure related adverse events such as deployment anomalies, branch lumen obstruction or occlusion, adverse events that result in secondary interventions for additional device implantation, and adverse events that result in conversion to open surgical repair.
- Reports provided to the DSMB will be submitted to the FDA as IDE supplements and a summary will be sent to each participating Site IRB.

The primary analysis will occur when enrollment is complete, and all available enrolled Subjects have completed the 1 month follow up assessment. A final DSMB review will be conducted when all enrolled Subjects have reached the 1 year follow-up window. Serial analyses of long-term results will occur during the follow-up period. No adjustments to the overall alpha level will be made since this is an exploratory study designed to evaluate basic feasibility.

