Tables (one for device migration and one for endoleak) will be prepared with time intervals and the incident event rate will be reported in each time interval window (using either the corresponding imaging date or adverse event onset date). Denominators for the time windows will be as specified in Section 5.1. An endpoint event (endpoint failure) will be reported from a Site-reported adverse event meeting the endpoint definitions. Time intervals for these tables will be the analysis windows shown in Table 1. In addition, endoleak rates will also be reported by endoleak type.

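### SAP 5.1 keeps imaged subjects with no Ascending Stent Graft in place in the migration and endoleak denominators, which modestly lowers both rates

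*Combined protocol and SAP*

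**What the plan says.** SAP 5.1 sets the base population: "All enrolled Subjects with an attempted initial procedure (have non-missing initial procedure date) will be included in analysis as follows". An attempt is enough; no implant is required.

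For migration and endoleak it adds one condition, applied window by window: "Subjects with known status (have had imaging done or endpoint event reported) at each follow-up window will be included". The only stated exclusion is: "Subjects without imaging reported in a window and with no endpoint event reported in window will not count towards the denominator for that window". The numerator comes from the sites: "an endpoint event (endpoint failure) will be reported from a Site-reported adverse event".

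SAP 5.3.5, which describes the two tables, adds no further restriction: "Denominators for the time windows will be as specified in Section 5.1".

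The plan also foresees subjects who may end without a graft. Technical success (SAP 2.3.2) has separate components for delivery, "Successful delivery of all required device components to the aorta and/or branch vessel", and for deployment, "Successful deployment of all required device components in their intended location". The DSMB reports in SAP 5.2 cover "adverse events that result in conversion to open surgical repair".

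**The concern.** Migration and endoleak are the secondary endpoints that describe whether the graft stays in position and seals. A reader will take each rate as the proportion of subjects with a graft in whom it moved or leaked. Under the rule as written, a subject with no graft who has a chest CTA in the window meets the known-status condition and adds one to the denominator, with no possibility of adding to the numerator. If the graft was never implanted, this happens in every window with imaging. If it was removed later, it happens in every such window after removal.

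The direction is unfavourable: the more subjects without a graft are imaged, the lower both rates become. SAP 2.4 plans no formal tests, so descriptive estimates with confidence intervals are the whole output, and their denominators need to mean what a reader will assume.

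**Working it through.** The visible text gives no expected rate, count or precision for these endpoints, so there is no planned figure to reproduce. The check is a reading of the rule followed by an illustration.

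**Reading**

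1. Entry to the population: attempted procedure (5.1).
2. Entry to the window denominator: imaging done or event reported in the window (5.1).
3. Exit from the window denominator: no imaging and no event in the window (5.1).
4. Further conditions in the analysis section: none visible; it refers back to 5.1 (5.3.5).
5. Removal or censoring after conversion or explant: none visible for these two endpoints.

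A graft-free subject with imaging passes steps 1 and 2 and is not caught by 3, 4 or 5.

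**Formula**

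Let n be the number in the window denominator under 5.1, x the number with an event, and k the number imaged with no graft in place and hence no possible event.

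- Rate as written: x/n.
- Rate among subjects with a graft in place: x/(n-k).
- Ratio of the first to the second: (n-k)/n.

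At n = 30 the ratio is 29/30 = 0.967 for k = 1, 27/30 = 0.900 for k = 3 and 25/30 = 0.833 for k = 5.

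**Numbers**

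n = 30 is the planned enrolment (SAP 2.2), so it is the largest possible denominator; n = 20 is an assumed smaller window. The values of x and k are assumptions. Intervals are exact (Clopper-Pearson) 95%.

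| n, x | As written | Graft in place, k = 1 | Graft in place, k = 5 |
|---|---|---|---|
| 30, 3 | 3/30 = 10.0% (2.1-26.5) | 3/29 = 10.3% (2.2-27.4) | 3/25 = 12.0% (2.5-31.2) |
| 30, 6 | 6/30 = 20.0% (7.7-38.6) | 6/29 = 20.7% (8.0-39.7) | 6/25 = 24.0% (9.4-45.1) |
| 20, 3 | 3/20 = 15.0% (3.2-37.9) | 3/19 = 15.8% (3.4-39.6) | 3/15 = 20.0% (4.3-48.1) |
| 30, 0 | 0% (upper limit 11.6) | 0% (upper limit 11.9) | 0% (upper limit 13.7) |

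For n = 30 and x = 3, the intermediate values are 3/28 = 10.7% (2.3-28.2) at k = 2 and 3/27 = 11.1% (2.4-29.2) at k = 3. At an observed 10%, the understatement is therefore 0.3 percentage points (10.3 - 10.0) for k = 1 and 2.0 points (12.0 - 10.0) for k = 5. With no events, only the upper confidence limit changes.

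**The case against.** Several objections have force.

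- **A restriction may sit in text that is not shown.** The endpoint definitions (2.3.3), Table 1, the imaging section (4.6), possibly part of 5.3.5, and the protocol body are missing from the public text. One could also argue that a subject without a graft has no migration status to know. This stands as a limit on confidence. Against it, 5.3.5 names 5.1 as the source of the denominator, and 5.1 spells out known status as imaging done or an event reported.
- **The subjects must be imaged.** The visible text does not say whether study CTA continues after a failed implant or a conversion. Those who die or are not imaged already drop out. This stands: the bias depends on k, which is unknown.
- **Not every failed delivery or deployment leaves the aorta without a graft.** A reader might infer that all technical failures dilute the rates. The documents do not support that. The components refer to all required parts and to the intended location, so a misplaced graft or a failed side branch component fails technical success while an Ascending Stent Graft remains at risk. Nor does listing conversion among the DSMB items say that the graft was removed.
- **Failures are reported elsewhere.** A reader might infer that failed cases vanish, that a worse device looks better overall, or that the objective of refining patient selection is defeated. That goes too far. Technical success includes every subject and counts missing evaluations as failures (5.1), and its components are summarised individually (5.3.2). Reinterventions are adjudicated by the CEC (5.5.5), and DSMB reports include deployment anomalies and conversions (5.2). What remains is that none of this corrects the two rates themselves.
- **In-situ rates have their own selection.** They describe only grafts still in place, so the choice is partly one of estimand. This is fair, and is why the number without a graft should stand beside each rate.

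**Conclusion.** The point holds in a limited form. On the visible text, imaged subjects with no Ascending Stent Graft in place count as non-events for migration and endoleak, and each rate is multiplied by (n-k)/n. The bias is always downward where k is above zero and there are events, and absent if every imaged subject has the graft.

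Its size is modest: about 0.3 to 2.0 percentage points at an observed 10% with n = 30 and k = 1 to 5, well inside the 95% interval. No formal decision depends on it. Only these two secondary rates are affected.

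The conclusion assumes that no in-situ condition appears in the sections not shown and that at least some graft-free subjects are imaged. Counts of events and of graft-free subjects are illustrative. Confidence is medium. The change is still worth making, because it is cheap and makes the denominators match what the rates will be taken to mean.

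**What to change.** In SAP 5.1 and 5.3.5:

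1. Limit the migration and endoleak denominators to subjects of known status with the Ascending Stent Graft implanted and still in place at the start of the window. State that a misplaced graft, or a failed side branch component with the Ascending Stent Graft in place, does not remove a subject.
2. Keep an event that precedes removal of the graft in the window where it occurred, and take the subject out of later windows. Event dating in 5.3.5 already supports the first half of this.
3. Beside each window's rate, give the number never implanted and the number explanted, so that the in-situ rate is not read as covering all attempted cases. The all-attempted rate may be shown as a supplement.

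The cost is SAP wording and one derived in-situ flag, programmed from the treatment, device accountability and reintervention data that SAP 4.1 and 5.5.5 already describe. The downside is slightly smaller denominators, slightly wider intervals and slightly less favourable rates. If the sections not shown already contain such a condition, a cross-reference from 5.1 is enough.

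### For device migration and endoleak, a subject without imaging can enter a window only as an event, so when such events occur the window rate describes no defined population

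*Combined protocol and SAP*

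**What the plan says.** SAP Section 5.1 sets the population for the two imaging endpoints window by window: "Subjects with known status (have had imaging done or endpoint event reported) at each follow-up window will be included". Two further sentences deal with subjects who have no imaging in the window. A subject with a qualifying event is kept, as an event: "Subjects without imaging reported in a window but with an adverse event meeting the endpoint definition in a window will count". A subject without one is dropped: "Subjects without imaging reported in a window and with no endpoint event reported in window will not count towards the denominator for that window". Section 5.3.5 carries the rule into the two endpoint tables: "Denominators for the time windows will be as specified in Section 5.1". Both sections take endpoint events from adverse events that the Site reports.

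Other tables use a different base. For the MACCE interval tables, Section 5.3.3 says: "Denominators for the time windows will be the number of Subjects remaining in follow-up as of the beginning of the time interval window". The adverse event summaries in Section 5.4 use the same type of denominator. Section 2.4 plans no formal tests: "Data will be presented descriptively with confidence intervals".

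The text of Sections 2.3.3, 4.6, 5.5.1, 8.1 and 8.2, Table 1, and possibly part of 5.3.5 is not shown in the public document. Nothing below treats that text as absent from the plan.

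**The concern.** A denominator limited to subjects whose status is known is sound when status can become known in either direction. Without imaging, this rule lets only one status become known, namely that an event occurred. Call a qualifying adverse event in a subject without imaging in that window an AE-only event. Each one adds a subject to numerator and denominator alike, while the comparable unimaged subject with no reported event adds nothing. Among the unimaged subjects who are included, the event rate is 100% by construction.

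At stake is what the reported figure means. With no tests planned, the window rates and their intervals are what the visible text offers for these two endpoints. A reader would take such a rate to refer to imaged subjects, or to all subjects still in follow-up. When AE-only events occur, it refers to neither.

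**Working it through.** The plan states no figure to reproduce. The only number taken from it is the 30 subjects (SAP Section 2.2). Imaging share, event risk and reporting share are assumptions, because the documents give none.

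**1. What each subject contributes under Section 5.1**

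| Subject in the window | Numerator | Denominator |
|---|---|---|
| Imaged, event | 1 | 1 |
| Imaged, no event | 0 | 1 |
| Not imaged, event reported | 1 | 1 |
| Not imaged, no event reported | 0 | 0 |

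With x events among n imaged subjects, a AE-only events, and N in follow-up at window start:
- planned rate = (x + a)/(n + a)
- imaged-only rate = x/n
- all in follow-up = (x + a)/N

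If a = 0, the planned and imaged-only rates are identical.

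**2. Expected value (ratio of expectations)**

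Let f be the share imaged, p1 and p0 the event risk in imaged and unimaged subjects, d the share of unimaged events reported as adverse events, and c the share of events in imaged subjects captured as adverse events.
- Planned rate = [f·p1·c + (1−f)·p0·d] / [f + (1−f)·p0·d]
- True rate = f·p1 + (1−f)·p0

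**3. Missing imaging unrelated to outcome, full capture (p1 = p0, c = 1)**

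For a true 20%, f = 0.8 and d = 0.5: (0.16 + 0.02)/(0.80 + 0.02) = 0.18/0.82 = 22.0%.

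| True rate, share imaged | d = 0 | d = 0.1 | d = 0.5 | d = 1 |
|---|---|---|---|---|
| 20%, 80% | 20.0% | 20.4% | 22.0% | 23.8% |
| 20%, 90% | 20.0% | 20.2% | 20.9% | 21.7% |
| 10%, 80% | 10.0% | 10.2% | 11.1% | 12.2% |

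Here the planned rate is too high whenever d > 0 and correct when d = 0.

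**4. Unimaged subjects at higher risk (p1 = 0.20, p0 = 0.40, f = 0.8, c = 1)**

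True rate = 0.16 + 0.08 = 24.0%.
- d = 0.1: 0.168/0.808 = 20.8%
- d = 0.5: 0.20/0.84 = 23.8%
- d = 1: 0.24/0.88 = 27.3%

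The direction changes where 0.16 + 0.08d = 0.24(0.80 + 0.08d), so d = 0.032/0.0608 = 0.53. The imaged-only rate is 20.0% throughout.

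**5. Events in imaged subjects under-reported (p1 = p0 = 0.20, f = 0.8, c = 0.9, d = 0.5)**

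Planned rate = (0.144 + 0.02)/0.82 = 0.164/0.82 = 20.0%, equal to the truth. Imaged-only = 0.144/0.80 = 18.0%.

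**6. How often the rule bites**

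With 6 unimaged subjects at 20% risk, the chance of at least one AE-only event in a window is 1 − (1 − 0.2d)^6, which is 11%, 47% and 74% for d = 0.1, 0.5 and 1.

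**7. Illustration**

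Take 30 in follow-up, 24 imaged with 3 events, and 6 unimaged with 1 AE-only event (95% Clopper-Pearson intervals):
- planned: 4/25 = 16.0% (4.5 to 36.1%)
- imaged-only: 3/24 = 12.5% (2.7 to 32.4%)
- all in follow-up: 4/30 = 13.3% (3.8 to 30.7%)

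**The case against.** The strongest reply is that the rule is explicit, errs on the cautious side in the simplest case, and keeps known device failures in the headline rate. That matches Section 5.1 elsewhere, where unknown 30-day mortality counts as death and missing technical success as failure. In step 4 the planned rate is closer to the truth than the imaged-only rate at every non-zero reporting level shown: errors of 3.2, 0.2 and 3.3 points against 4.0. In step 5 it is exact and imaged-only is 2 points low. All of this stands. It rules out replacing the planned rate by the imaged-only rate, but it does not give the planned rate a population, and its accuracy in steps 4 and 5 depends on errors that offset.

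It is also fair to say that AE-only events may be few, that the effect is small, and that Section 5.5.1 or the table and listing sections may already supply the extra figures. All three are accepted.

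A reader might infer more than the documents support:
- *That the plan overstates migration and endoleak.* This needs missing imaging unrelated to outcome, full capture of events in imaged subjects, and at least some AE-only reporting. The documents establish none of these.
- *That no sensitivity analysis, imaged count or listing is planned.* The text that would show this is not visible.
- *That counting all unimaged subjects as events, 9/30 = 30.0% in the illustration, is a strict upper bound.* It is not, because an event in an imaged subject that is never reported as an adverse event would still be missed.

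**Conclusion.** The point holds as a matter of definition. Under Sections 5.1 and 5.3.5, once an AE-only event occurs, inclusion in that window depends on the outcome, and the rate and its interval refer to no defined population. This needs no assumption beyond the occurrence of such an event.

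The direction and size of any error do rest on assumptions. If missing imaging is unrelated to outcome and capture in imaged subjects is complete, the excess over a true 20% with 80% imaged runs from 0.4 points (one in ten unimaged events reported) to 3.8 points (all reported). Outside those conditions the error can go either way.

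Severity is minor. In the illustration the 3.5-point gap is one subject, well inside either interval. These are secondary endpoints presented descriptively, Section 5.2 states that "this is an exploratory study designed to evaluate basic feasibility", and neither the primary endpoint nor any decision rule visible in the documents is affected.

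**What to change.** In Sections 5.1 and 5.3.5, keep the planned rate and label it as including AE-only events. Beside it, for each endpoint and window, report the following unless sections not shown already provide them:
- (a) the rate among subjects with imaging in that window, with its confidence interval;
- (b) the number in follow-up who were not imaged, and the number of AE-only events;
- (c) all reported events over all subjects in follow-up at window start, the denominator type already used for MACCE and adverse events. Label this a lower figure, since it treats every unimaged subject with no reported event as event-free.

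In the illustration the row would read: planned 4/25 = 16.0%; imaged-only 3/24 = 12.5%; 6 not imaged, 1 AE-only event; all in follow-up 4/30 = 13.3%.

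Imaged-only should not become the sole main rate. If a figure counting all unimaged subjects as events is added, it should not be called a strict upper bound.

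The cost is SAP wording and two or three extra figures per window, with no new data. The downside is more than one rate to read, so the labels must say which subjects each one covers.
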